7.1.3.3 Non-Clinical Evidence for Activity of Eribulin in Pediatric Sarcomas

The potential antitumor activity of eribulin in human pediatric tumor models was evaluated in the NCI's Pediatric Preclinical Testing Program (PPTP; Study Nos. PPC-2-12-02N submitted to IND 067193, sequence 0636 and PPC-2013-01N submitted to IND 067193, sequence 0652). In the 24 cell line in vitro screening panel, eribulin demonstrated potent cytotoxic activity with a median relative half maximal inhibitory concentration value of 0.27 nM (range: <0.10 to 14.8 nM). The panel included 4 RMS (RD, Rh18, Rh30, and Rh41) and 4 EWS cell lines. The in vitro pattern of activity for eribulin was similar to that previously described by the PPTP for vincristine (Kolb, et al., 2013).

In the PPTP's in vivo panel of 43 human pediatric tumor xenografts, eribulin induced significant differences in event-free survival (EFS) distribution compared with control in 26 of 30 (83%) of the evaluable solid tumor xenografts and in 8 of 8 (100%) of the evaluable acute lymphoblastic leukemia (ALL) xenografts. An objective response was observed in 18 of 35 (51%) solid tumor xenografts. Complete responses (CRs) or maintained CRs (MCRs) were observed in 6 of 7 RMS xenograft models (Rh28, Rh30, Rh30R, and Rh41 cells). CRs or MCRs were also observed in 1 of 2 Wilms' tumor, 4 of 5 EWS, 2 of 4 glioblastoma, and 3 of 6 osteosarcoma xenografts. For the ALL panel, all 8 xenografts achieved CR or MCR (Kolb, et al., 2013).

The PPTP concluded that the high level of activity observed for eribulin against the PPTP preclinical models made eribulin an interesting agent to consider for pediatric evaluation. The activity pattern observed for eribulin in the solid tumor panels is comparable or superior to that observed previously for vincristine. Eribulin showed high activity against RMS, EWS, osteosarcoma, and ALL xenografts (Kolb, et al., 2013).

7.2 Study Rationale

The unique survival advantage seen in Study 309, and the activity of eribulin seen in both Studies 207 and 217, suggests that it is desirable to pursue development in pediatric sarcomas. However, the potential differences in the sensitivity of specific tumor subtypes to microtubule inhibition make it difficult to justify development of eribulin in pediatric

populations based on the clinical antitumor activity in adults alone. Strong supportive evidence from nonclinical studies is provided in [Section 7.1.3.3](#).

In addition to the encouraging results seen in the PPTP, and the unique survival advantage observed in adult liposarcoma subtype, the aim of eribulin development in childhood sarcoma is also based upon and the unmet medical need in advanced RMS, EWS, and NRSTS. Eribulin may offer a potential new alternative to the available therapies for children who have failed standard treatments for advanced RMS, EWS, and NRSTS.

A Phase 1 study (Eisai Study E7389-A001-113, Study 113) of eribulin mesylate in pediatric patients with recurrent or refractory solid tumors (excluding CNS), including lymphomas has been conducted. The MTD was determined to be 1.4 mg/m², which is the same dose as in the adult population. No major differences were observed in the safety profile between adults and pediatric subjects ([Schafer, et al., 2018](#)).

8 STUDY OBJECTIVES

8.1 Primary Objective

The primary objectives of the study are:

- To conduct a preliminary assessment of activity of eribulin mesylate in pediatric subjects with relapsed/refractory RMS, NRSTS or EWS to determine whether each cohort warrants further investigation.

8.2 Secondary Objectives

The secondary objectives of the study are:

- To evaluate the PFS, using Response Evaluation Criteria in Solid Tumors (RECIST) 1.1, of eribulin mesylate in pediatric subjects with relapsed/refractory RMS, NRSTS, or EWS in all cohorts combined.
- To evaluate the safety and tolerability of eribulin in the pediatric subjects with relapsed/refractory RMS, NRSTS, or EWS in all cohorts combined.
- To evaluate the duration of response (DOR) of eribulin mesylate in pediatric subjects with relapsed/refractory RMS, NRSTS, or EWS.
- To evaluate the overall survival (OS) of pediatric subjects with relapsed/refractory RMS, NRSTS and EWS.

8.3 Exploratory Objective(s)

- To evaluate the exposure of eribulin mesylate in pediatric subjects with relapsed/refractory RMS, NRSTS, or EWS.
- To explore the relationship between exposure to eribulin mesylate and AEs and efficacy.

9 INVESTIGATIONAL PLAN

9.1 Overall Study Design and Plan

E7389-G000-223 is a Phase 2, multicenter, open-label study to conduct a preliminary assessment of the safety and activity of eribulin mesylate in pediatric subjects with relapsed/refractory RMS, NRSTS, or EWS.

Forty-five pediatric subjects, with approximately 15 subjects each with RMS, NRSTS, or EWS, will be enrolled to receive eribulin mesylate as an intravenous (IV) infusion at a dose of 1.4 mg/m² (Recommended Phase 2 Dose [RP2D]) on Days 1 and 8 of each 21-day cycle as determined by the dose finding study ADVL1314 (Eisai Study E7389-A001-113).

Outline

- Pediatric subjects with relapsed/refractory RMS, NRSTS or EWS will be enrolled to receive therapy with eribulin mesylate.
- For each histology type, approximately 15 subjects will be treated. Data will be monitored on an ongoing basis; depending on evaluation by the investigators and sponsor, if sufficient responses (PRs or CRs) are observed, then this histology type will be recommended for inclusion in the subsequent study.
- Subjects will continue study therapy until progression of disease (per RECIST 1.1), intolerable toxicity or withdrawal of consent.

Pre-study Phase:

Day -28 to -1, computed tomography (CT) / magnetic resonance imaging (MRI) scans must be performed within 28 days prior to study drug administration. All clinical and laboratory test results to determine eligibility must be performed within 7 days prior to study drug administration, unless otherwise indicated.

Treatment Phase:

The treatment phase will start on Day 1 of Cycle 1.

Follow-up:

The follow-up period will begin immediately after the End of Treatment visit until death or informed consent is withdrawn, unless the study is terminated by the sponsor. Subjects will be followed for survival approximately every 12 weeks for 1 year and then annually thereafter. As well as follow-up for survival, the annual surveillance will also assess any long term effects of the study treatment.

During the follow-up period, subjects who have gone off study treatment without progression should have tumor assessments every 6 - 12 weeks, at the investigator's discretion, from the date of last tumor assessment until disease progression is documented, death, or initiation of

another anticancer therapy, whichever occurs first, unless the study is terminated by the sponsor. Follow-up data will be required unless consent is withdrawn.

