- Pediatric subjects with relapsed/refractory RMS, NRSTS or EWS will be enrolled to receive therapy with eribulin mesylate.
- For each histology type, approximately 15 subjects will be treated. Data will be monitored on an ongoing basis; depending on evaluation by the investigators and sponsor, if sufficient responses (partial response [PR] or complete response [CR]) are observed, then this histology type will be recommended for inclusion in the subsequent study.
- Subjects will continue study therapy until progression of disease (per RECIST 1.1), intolerable toxicity or withdrawal of consent.

Pre-study Phase:

Day -28 to -1, computed tomography (CT) / magnetic resonance imaging (MRI) scans must be performed within 28 days prior to study drug administration. All clinical and laboratory test results to determine eligibility must be performed within 7 days prior to study drug administration, unless otherwise indicated.

Treatment Phase:

The treatment phase will start on Day 1 of Cycle 1.

Follow-up:

The follow-up period will begin immediately after the End of Treatment visit until death or informed consent is withdrawn, unless the study is terminated by the sponsor. Subjects will be followed for survival approximately every 12 weeks for 1 year and then annually thereafter. As well as follow-up for survival, the annual surveillance will also assess any long term effects of the study treatment.

During the follow-up period, subjects who have gone off study treatment without progression should have tumor assessments every 6-12 weeks, at the investigators discretion, from the date of last tumor assessment until disease progression, death, or initiation of another anticancer therapy, whichever occurs first, unless the study is terminated by the sponsor. Follow-up data will be required unless consent is withdrawn.

Number of Subjects

The target enrollment is 45 subjects.

Inclusion Criteria

Subjects must meet all of the following criteria to be included in this study:

1. Age: ≥ 12 months to < 18 years old at the time of informed consent.
2. Diagnosis: Histologically confirmed RMS, NRSTS (Grade 2 or 3) or EWS which is relapsed or refractory (failed front line therapy).
3. The presence of measurable disease meeting the following criteria:
 - At least 1 lesion of ≥ 1.0 cm in the longest diameter for a non-lymph node or ≥ 1.5 cm in the short-axis diameter for a lymph node that is serially measurable according to RECIST 1.1

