9.3.3 Removal of Subjects From Therapy or Assessment

The investigator may discontinue treating a subject with study treatment or withdraw the subject from the study at any time for safety or administrative reasons. The subject may decide to discontinue study treatment or withdraw from the study at any time for any reason. The reason for discontinuation will be documented. If a subject discontinues study treatment, the subject will enter the Follow-Up Period and complete protocol-specified off-treatment visits, procedures, and survival follow-up unless the subject withdraws consent. The investigator should confirm whether a subject will withdraw from study treatment but agree to continue protocol-specified, off-treatment study visits, procedures, and survival follow-up, or whether the subject will withdraw consent. If a subject withdraws consent, the date will be documented in the source documents. A subject removed from the study for any reason other than toxicity or progression may be replaced.

During the Follow-Up Period, subjects who have discontinued study treatment without progression should have disease assessments as per the Schedule of Assessments from the date of the last assessment until disease progression as per RECIST 1.1 is documented, death or another anticancer therapy is initiated.

All subjects will be followed for survival until death, except where a subject withdraws consent or the sponsor chooses to halt survival follow-up after completion of the primary study analysis.

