9.5.1.4 Tumor Assessments

Tumor response and progression will be evaluated according to RECIST 1.1 criteria. Copies of all scans for tumor assessments will be sent to an imaging core laboratory designated by the sponsor. Tumor assessments will be carried out following the guidelines provided by the imaging core laboratory. Decisions concerning treatment discontinuation for PD will be based on investigator assessment.

Tumor assessments (CT chest, and CT or MRI abdomen, pelvis, and other known or suspected sites or disease) will be performed during screening and then every 6 weeks (within the sixth week) on a fixed schedule from the date of first study drug administration. Magnetic resonance imaging (MRI) scans may be used instead of CT scans for abdomen and pelvis; however, chest must be assessed using CT. The same method of assessment must be used at all time-points as used at pre-study. Partial and complete responses will be confirmed at least 4 weeks after initial documentation of PR or CR, typically on the next consecutive scheduled tumor assessment. After 24 weeks subjects with CR, PR or stable disease (SD) may have imaging decreased to every 9 weeks (within the ninth week). A bone scan using whole body bone MRI, ^{99m}m-technetium based bone scans, ¹⁸F-fluorodeoxyglucose (FDG)-PET/CT scans or ¹⁸F-sodium fluoride positron emission tomography [NaF PET] will be performed during screening to establish a baseline (a historical bone scan performed within 6 weeks before study drug administration is acceptable), approximately every 24 weeks (in

conjunction with a scheduled tumor assessment visit), and as clinically indicated. Lesions identified on bone scans should be followed with cross-sectional imaging.

Brain scans will be performed as clinically indicated to assess potential CNS disease and/or metastases. For subjects with a history of protocol-eligible treated brain metastases, a brain scan will be required at screening and all tumor assessment time points (eg, every 6 weeks).

Subjects who discontinue treatment without objective evidence of disease progression will continue to have tumor assessments performed, per the schedule of assessments, until disease progression, death, or initiation of another anticancer therapy.

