- j. Pre-study phase: Screening tumor assessments using CT of the chest/abdomen and pelvis and other areas of known disease or newly suspected disease should be performed between Day -28 and Day -1. Detailed image acquisition guidelines will be provided by the imaging core laboratory. Scans that were performed within this window but before informed consent may be used if they were acquired consistent with the guidelines provided by the imaging core laboratory. Scans of the abdomen, pelvis, and other areas of the body may be done with MRI instead of CT, but evaluation of the chest must be done with CT.

Treatment phase: Tumor assessments of the chest, abdomen, and pelvis and other areas of known disease that were scanned at screening, or newly suspected disease, must be performed every 6 weeks (within Week 6) during Treatment Cycles, counting from the date of first dose (or sooner if there is evidence of progressive disease) until Week 24 and then every 9 weeks (or sooner if clinically indicated) thereafter and should utilize the same methodology (CT/MRI) and scan acquisition techniques (including use or nonuse of IV contrast) as were used for the screening assessments. A chest x-ray or skeletal x-ray that clearly demonstrates a new metastatic lesion may be used to document progression in lieu of the CT/MRI scans.

Follow-Up Period: Subjects who have gone off study without progression should have tumor assessments every 6 weeks from the date of last tumor assessment until disease progression or initiation of another anti-cancer therapy. At week 24 and thereafter, these scans may be conducted every 9 weeks.

- k. Pre-study phase: Screening CT or MRI of the brain should be performed between Day -28 and Day -1 for subjects with previously treated protocol-eligible brain metastases only.
- For subjects with previously treated protocol-eligible brain metastases, a brain scan must be performed at all tumor assessment time points. The same methodology and scan acquisition techniques used at screening should be used throughout the study to ensure comparability.
- l. Bone scans may be performed, where indicated, using ⁹⁹Tc based bone scans, NaF (PET) bone scans, ¹⁸F-FDG-PET/CT scans or whole body bone MRI. The same methodology used at screening should be performed at all subsequent bone assessments.
- m. Subjects will be followed for survival approximately every 12 weeks from the end of treatment for 1 year, unless consent is withdrawn or death

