8 DEFINITIONS AND CONVENTIONS FOR DATA HANDLING

Censoring Rules for PFS/DOR

The PFS censoring rules in this SAP and definition of progression date follow the Food and Drug Administration (FDA) “Guidance for Industry Clinical Trial Endpoints for the Approval of Cancer Drugs and Biologics (2007)”.

Table 1 Censoring Rules for Progression-free Survival Endpoint

Situation	End Date	Censored
Investigator documented PD	Date of the first assessment of the series of radiologic tests that determined PD	No
Death during the study before first PD	Date of death	No
No baseline or post-baseline tumor assessments	Date of first dose	Yes
No progression and no death at the time of data cutoff	Date of last adequate tumor assessment* prior to data cutoff	Yes
Non-study anticancer treatment initiated before progression or death	Date of last adequate tumor assessment* prior to or on date of non-study anticancer treatment	Yes
Death or progression after more than one missed tumor assessments**	Date of last adequate tumor assessment* prior to missed tumor assessments	Yes

PD = progressive disease.

* Adequate tumor assessment is radiologic assessment of CR, PR, SD, non-CR/non-PD or PD as determined by investigators at regular interval as defined in the protocol. Any tumor assessments after new anticancer treatment starts will be removed in the definition of PFS.

**More than one missed visit/adequate tumor assessment is defined as having the duration between the last adequate tumor assessment and PD or death being longer than the gap limit.

a) The gap from baseline to the 1st assessment post-baseline (calculated from C1D1), gap limit = 2*6 weeks + 2*3 Days = 90 days.

- b) The gap from the 1st assessment post-baseline, or from any later assessment -- call it "previous assessment", to the next assessment.
- if Study Day of the previous assessment < (18 weeks - 3 days), then gap limit = 2*6 weeks + 2*3 days = 90 days;
 - if (18 weeks - 3 days) <= Study Day of the previous assessment < 24 weeks - 3 days, then gap limit = 6 weeks + 9 weeks + 2*3 days = 111 days;
 - if Study Day of the previous assessment >= 24 weeks - 3 days, the gap limit = 2*9 weeks + 2*3 days = 132 days.

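### Two off-treatment scan schedules stand in the current text, and the SAP's missed-scan censoring limits fit only one of them

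*Protocol*

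**What the plan says.** Two wordings cover subjects who have stopped treatment without progression. Both are current text, not entries in the revision history.

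- **6 to 12 weeks, at discretion.** Protocol 9.1 (Follow-up) says they "should have tumor assessments every 6 - 12 weeks, at the investigator's discretion". The synopsis has the same rule: "without progression should have tumor assessments every 6-12 weeks, at the investigators discretion". SAP 3.2 repeats it.
- **6 weeks, optionally 9 from Week 24.** Table 9 footnote j (Follow-Up Period) reads "Subjects who have gone off study without progression should have tumor assessments every 6 weeks from the date of last tumor assessment", and then "At week 24 and thereafter, these scans may be conducted every 9 weeks". An interval of 12 weeks is not offered.

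Other sections lead to footnote j without restating an interval. Protocol 9.3.3 says such subjects "should have disease assessments as per the Schedule of Assessments", and 9.5.1.4 says they "will continue to have tumor assessments performed, per the schedule of assessments, until disease progression". The efficacy assessments part of the synopsis also defers to the schedule of assessments, so the synopsis points both ways. Protocol 9.5.1.3.2, which describes the PFS assessments, gives 6 weeks until Week 24 and 9 weeks after that. No text says which wording takes precedence.

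SAP section 8 dates progression at the scan that shows it. It censors a progression or death that follows more than one missed assessment, and it turns this into a maximum gap since the last adequate assessment. The first limit is "gap limit = 2*6 weeks + 2*3 Days = 90 days"; the other two are 111 and 132 days. An adequate assessment is one made at the regular interval that the protocol defines.

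**The concern.** A site that scans an off-treatment subject every 12 weeks complies with Protocol 9.1 and departs from Table 9. The SAP repeats the wider interval in its design section but builds its censoring limits as though only 6 and 9 weeks existed. Two things then depend on which section a site follows: the date on which progression is recorded, and whether a progression or death counts as an event or is censored. The second matters more, because the limits are meant to act only after more than one missed assessment. Both PFS and DOR are exposed, since the section 8 rules are headed as applying to both.

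**Working it through.** **Inputs.** Schedule A is 42 to 84 days (synopsis, Protocol 9.1, SAP 3.2). Schedule B is 42 days, with an option of 63 days from Week 24 (footnote j). SAP section 8 chooses the limit by the study day of the previous assessment, with cut-points at 18 weeks − 3 days = 126 − 3 = Day 123 and 24 weeks − 3 days = 168 − 3 = Day 165.

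**1. The SAP's own limits.** 2×42 + 2×3 = 90. 42 + 63 + 2×3 = 111. 2×63 + 2×3 = 132. All three reproduce exactly. Each is two scheduled intervals plus a 6-day allowance, with intervals of 6 and 9 weeks only.

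**2. The rule applied to each spacing.** With one scan missed, progression is found at the following scan, two intervals after the last adequate one.

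| Last adequate scan | Limit (days) | Footnote j, one missed | 9-weekly, one missed | 12-weekly, one missed | 12-weekly, none missed: margin |
|---|---|---|---|---|---|
| Before Day 123 | 90 | 2×42 = 84, event | 2×63 = 126, censored | 2×84 = 168, censored | 90 − 84 = 6 |
| Day 123 to before Day 165 | 111 | 42 + 63 = 105, event | 126, censored | 168, censored | 111 − 84 = 27 |
| Day 165 onward | 132 | 2×63 = 126, event | 126, event | 168, censored | 132 − 84 = 48 |

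Under footnote j, one missed scan never leads to censoring. Under 12-weekly scanning it does so in every window, and under 9-weekly scanning it does so if the last scan was before about Week 24.

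**3. No scan missed, but one late.** In the first window a 12-weekly scan done 7 days late falls at 84 + 7 = 91 days, which exceeds 90, so a progression seen on it is censored. Under a 6-week interval the margin is 90 − 42 = 48 days.

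**4. Deaths.** The limit runs from the last adequate scan to the death. With one 12-weekly scan missed at 84 days and the next not due until 168, a death from day 91, 112 or 133 onward (by window) is censored. Under footnote j, a death up to the next due scan (84, 105 or 126 days) stays within the limit.

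**5. Recorded date of progression.** As a rough guide, the mean delay from true to recorded progression is half the interval: 21 days at 6 weeks, 31.5 at 9 and 42 at 12. The excess of 12-weekly over footnote j is therefore 42 − 21 = 21 days before Week 24, and 42 − 31.5 = 10.5 days after it if the 9-week option is used. A simulation assumed exponential time to progression from the last on-treatment scan (Day 42, 84 or 168), with medians of 6, 12 and 24 weeks. These medians are assumptions; the documents give none. The mean delay was 3.6 to 5.3 weeks under footnote j and 6.3 to 7.4 weeks under 12-weekly scanning. Scenario by scenario, the excess was 1.7 to 3.8 weeks per affected subject (smallest 6.35 − 4.69 = 1.66; largest 7.35 − 3.60 = 3.75).

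**The case against.** The strongest reply is that most of the text already agrees. Footnote j, the sections that refer to it, 9.5.1.3.2 and the SAP limits all fit 6 and 9 weeks. A site following footnote j also satisfies the 6 to 12 week wording. The schedules part only when a site goes beyond 6 weeks before Week 24, or beyond 9 weeks after it. Footnote j is not strictly fixed either, because the move to 9 weeks is optional. All of this stands. It narrows the conflict but does not remove it: nothing ranks the passages, and the SAP itself carries the wider wording.

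It is also true that a 12-weekly scan done on time, at 84 days, is inside even the shortest limit. A reader might infer that following Protocol 9.1 leads to censoring by itself. It does not; a late or missed scan is needed, and the 6-day margin applies only in the first window.

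A reader might set the 3-week difference in half-intervals against the adult liposarcoma PFS medians in Protocol 7.1.3.2 (21/88.3 = 24% of 2.9 months, 21/51.7 = 41% of 1.7 months) and infer a shift of that order in this trial. The documents do not support that. The 1.7 months belongs to the dacarbazine arm. Both medians describe whole adult populations, whereas the delay applies to a subset here. Subjects still on treatment have 6-weekly scans up to Week 24 whichever follow-up wording is used.

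A reader might also infer that investigators would steer progression dates, or that PFS and DOR must be inflated. The documents give no evidence of steering. Later detection does lengthen recorded times, but censoring removes follow-up as well as an event, so its net direction on a Kaplan-Meier median is not fixed.

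Finally, PFS and DOR are secondary, descriptive estimates pooled over cohorts in a single-arm study, and the decision on each cohort rests on confirmed responses. That limits the consequence.

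**Conclusion.** The point holds as an inconsistency with a definite analytic effect. The current text gives two off-treatment schedules, and the SAP limits match only the 6 and 9 week one. At 12-weekly spacing, one missed scan is enough for a progression or death to be censored under a rule meant for more than one. With a last scan before about Week 18, a progression scan 7 days late is enough. Nine-weekly spacing before about Week 24 has the same fault after one missed scan. The gap results are exact arithmetic on the documents' figures; the 1.7 to 3.8 week delay rests on the assumed progression times.

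The effect is confined to subjects who stop without progression and start no other anticancer therapy. Their number is not given, so the shift in median PFS or DOR cannot be computed, and the point does not reach the primary response endpoint. It should be corrected, but it does not threaten the trial's main conclusion.

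**What to change.** Reconcile both places in the synopsis, Protocol 9.1, 9.3.3, 9.5.1.3.2, 9.5.1.4, Table 9 footnote j and SAP 3.2 to one off-treatment assessment schedule. The choice of schedule is the sponsor's. Then derive the SAP section 8 gap limits from that schedule, so that censoring applies only after more than one missed assessment. If a range of intervals is kept, the limits must accommodate the longest interval allowed. The cost is a protocol clarification and SAP wording, with the matching change to the censoring derivation.
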